### 6.4.2. Suicide Risk Management Plan

The protocol procedures related to clinical care of patients with treatment-emergent suicidal ideation and behavior must be implemented to ensure proper management of the event and protection of subject's safety. If a disclosure of suicidal ideation is revealed as part of the C-SSRS questionnaire or when a subject spontaneously expresses that he/she may be a threat to him/herself, the study team should be prepared to quickly evaluate the event and to determine the appropriate course of action.

# 6.4.2.1. Assessment of Suicide Risk

Any indication of suicidal ideation should be evaluated as soon as possible by appropriately trained staff. The Investigator is responsible for making the final judgment regarding potential suicide risk and need subsequent action.

### 6.4.2.2. Acute Suicidal Crisis

A person evaluated as being at high risk should be transferred to an immediate care facility. The Investigator will guide intervention as clinically indicated and follow up with the subject within 1 week and/or refer him/her to a qualified mental health professional.

### 6.4.2.3. Non-acute Suicidal Risk

The Investigator will conduct safety planning with the subject and will follow up within 1 week.

Reference materials for subjects and caregivers should include lists of mental health organizations and professionals, outpatient behavioral services, local crisis and peer support groups and Suicide/Crisis Hotlines.

#### 6.5. Clinical Measurements

#### 6.5.1. Clinical Safety Laboratory Assessments

With the exception of urine pregnancy tests and urine drug screen tests, clinical laboratory tests are performed by a central laboratory as specified in the reference binder.

Details for collecting, handling, and shipping samples (including shipment addresses) are detailed in a separate clinical laboratory manual. The Schedule of Events and Assessments (Table 1 [SCHEDULE 'A'] or Table 2 [SCHEDULE 'B']) shows the time points at which blood and urine samples are collected. Table 3 presents the clinical laboratory tests to be performed.

Category	Parameters						
Serology	Human immunodeficiency virus (HIV)-1, HIV-2, hepatitis B, hepatitis C; Visit 'S', SCHEDULE 'B' only						
Hematology	Red blood cell count, hemoglobin, hematocrit, platelet count, and WBC count with differential						
Chemistry	Electrolytes: Chloride, phosphate, potassium, sodium						
	Liver function tests : Alkaline phosphatase, aspartate aminotransferase, alanine aminotransferase, total bilirubin, direct bilirubin						
	Renal function parameters: Blood urea nitrogen, creatinine						
	Other: Glucose, Ca +2 , albumin, total protein, bicarbonate						
	FSH: Post-menopausal females only						
Urinalysis	Macroscopic examination a , pH, specific gravity, protein, glucose, ketone, occult blood, WBC, nitrites, bilirubin, urobilinogen						
Serum Drug Screen	Ethanol; Visit 'S', SCHEDULE 'B' only						
'Standard' Urine Drug Screen (UDS)	amphetamines, barbiturates, benzodiazepines, buprenorphine, cocaine, ecstasy, methadone, methamphetamine, opiates, oxycodone, phencyclidine, propoxyphene, tricyclic antidepressant, THC (cannabinoids); Visit 'S', SCHEDULE 'B' only						
Point of Care Urine Drug Screen	Test 1 : amphetamines, barbiturates, benzodiazepines, buprenorphine, cocaine, ecstasy, methadone, methamphetamine, opiates, oxycodone, phencyclidine, propoxyphene, tricyclic antidepressant, THC (cannabinoids).						
	Test 2: methylphenidate						
On site Urine Pregnancy Test (at all study visits)	FOCP only						
Home Urine Pregnancy Test (in between study visits following study visit 3)	FOCP only (dispense home pregnancy kit at Study Visits 3 thru 21)						

Table 3	Clinical Laboratory Tests
---------	---------------------------

FOCP = females of childbearing potential; FSH = follicle stimulating hormone; WBC = white blood cell aA microscopic examination will be performed on abnormal findings unless otherwise specified.

# 6.5.2. Vital Signs and Weight

Vital signs measurements (e.g., orthostatic blood pressure/heart rate, oral temperature, and respiratory rate) and body weight is obtained at the time points shown in Schedule of Events and Assessments (Table 1 [SCHEDULE 'A'] or Table 2 [SCHEDULE 'B']). Orthostatic blood pressure/heart rate are measured after the subject has been sitting for at least 5 minutes and again within 3 minutes of subject standing. Vital signs may be taken at any other time, as deemed necessary by the Investigator.

# 6.5.3. Physical Examinations and Height

Physical examinations are obtained at the time points shown in the Schedule of Events and Assessments (Table 1 [SCHEDULE 'A'] or Table 2 [SCHEDULE 'B']). The physical examination conducted at the initial study visit will include assessments of all body systems except genitourinary. Any findings during initial study visit in this study (prior to first dose of OLE SM) will be recorded as medical history and any clinically significant abnormal findings during treatment period (after the first dose of OLE SM until the end of the study) will be recorded as an AE. For the physical examination at EOS, only changes from the initial study visit of this study (812P311) will be noted.

# 6.5.4. Electrocardiograms (ECGs)

A 12-lead ECG will be obtained at the time points shown in the Schedule of Events and Assessments (Table 1 [SCHEDULE 'A'] or Table 2 [SCHEDULE 'B']). Additional ECGs may be performed at other times if deemed necessary by the Investigator.

The ECG will be recorded while the subject is resting in a supine position for at least 10 minutes. The ECG will electronically measure the PR, QRS, QT, and QTc intervals, and heart rate. All ECG tracings will be reviewed within 24 hours by the Investigator or qualified Sub-investigator. PR intervals will be determined for each of these ECGs from a single reading. Invalid measurements will be repeated. QTc will be reported as QTcF (QT corrected using Fridericia's method).

# 6.6. Screening Scales and Assessment Tools

# 6.6.1. Structured Clinical Interview for DSM-5, Clinical Trials (SCID-5-CT)

The Structured Clinical Interview for DSM-5 (SCID-5) is a semi-structured interview guide for making the major DSM-5 diagnoses (Spitzer et al., 1992; First et al., 2015)

). It is administered by a clinician or trained mental health professional who is familiar with the DSM-5 classification and diagnostic criteria. The Clinical Trials version (SCID-5-CT) is an adaptation of the Research version (SCID-5-RV) that has been reformatted, streamlined, and optimized for use in clinical trials that incorporate typical inclusion and exclusion criteria. The SCID is broken down into separate modules corresponding to categories of diagnoses, including ADHD. Most sections begin with an entry question that would allow the interviewer to "skip" the associated questions if not met. For all diagnoses, symptoms are coded as present, subthreshold, or absent. A diagnosis of ADHD is made following the post-traumatic stress disorder diagnostic algorithm. Only administered SCID-5-CT to *de novo* subjects (Visit 'S' [SCHEDULE 'B']).

# 7. STATISTICAL METHODS

### 7.1. General Considerations

In general, continuous variables will be summarized with standard descriptive statistics including number of subjects (n), mean, standard deviation (SD), median, minimum, and maximum. Categorical variables will be summarized with frequencies and percentages.

The data summaries will be accompanied by individual subject data listings, as specified in Sections 16.2 and 16.4 of ICH Guidance E3, sorted by unique subject identifier. All data available from the eCRFs will be listed. Unscheduled measurements will be excluded from the descriptive statistics and statistical analysis but will be included in listings.

Additional details of the statistical analysis will be provided in a separate statistical analysis plan (SAP). The statistical analysis methods described in the SAP will supersede the statistical methods described in this protocol.

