### 5.1.7. Unscheduled Visits

At the discretion of the investigator throughout the study, unscheduled visits may be conducted to perform or repeat assessments, including ECG, measure vital signs and weight, draw blood sample for hematology and/or serum chemistry or serum pregnancy test (FOCP), obtain urine sample for urine pregnancy test and/or urine drug screen (POC [if applicable]; see Table 3), administer C-SSRS ('Since Last Visit' version), perform physical examination. AEs, concomitant medications and 'caffeine use' should also be assessed at all unscheduled visits. SM may also be dispensed and/or returned at unscheduled visits, if needed.

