4.5.3 Laboratory Data

4.5.3.1 Potentially Clinically Significant Laboratory Values

The number and percentage of subjects with PCS values post-baseline will be summarized for the hematology and chemistry parameters defined in Table 1 and Table 2. All scheduled and unscheduled results will be included in this laboratory analysis.

Hematology parameter	Potentially clinically significant values
Hemoglobin	Female: <85 g/L or >160 g/dL)
	Male: <90 g/L or >170 g/L)
Hematocrit (HCT)	Hematocrit (Female) ≤32% or >49 %
	Hematocrit (Male) ≤37% or >48 %
Platelet count	<125 x 10^9/L or >470 10^9/L
White blood cells (WBC)	<2.0 x 10^9/L or >12.0 10^9/L
Basophils	>0.5 x 10^9/L
Eosinophils	>1.5 x 10^9/L
Lymphocytes	<0.5 x 10^9/L or >6.0 10^9/L
Monocytes	>1.6 x 10^9/L
Neutrophils	<1.5 x 10^9/L

Chemistry parameter	Potentially clinically significant values
Alanine aminotransferase	>3 x upper limit of normal (ULN)
(ALT)	
Albumin	<22 g/L or >65 g/L
Aspartate aminotransferase	>3 x ULN
(AST)	
Alkaline Phosphatase (ALP)	>3 x ULN
Bilirubin	>2 x ULN
Blood urea nitrogen (BUN)	>9.6 mmol/L
Calcium	<2.0 mmol/L or >2.75 mmol/L
Chloride	<90 mmol/L or >120 mmol/L
Creatinine	> 1.3 mg/dL or >115 µmol/L
Potassium	<3 mmol/L or >5.8 mmol/L
Sodium	<125 mmol/L or >158 mmol/L
Protein	<45 g/L
Glucose	non-fasting < 2.2 mmol/L or >8.9 mmol/L

Abnormally low or high laboratory results based on the laboratory normal ranges will be presented in a data listing.

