4.5.3.2 Abnormal Liver Enzymes and Liver Function Values

Summaries of abnormal liver enzymes and liver function tests post-baseline will be presented for ALT, AST, Direct Bilirubin, Total Bilirubin, and ALP. All scheduled and unscheduled results will be included in these analyses.

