4.5.4 Vital Signs

The number and percentage of subjects with abnormally low or high vital sign values postbaseline based on the normal ranges defined in Table 3 will be presented. All scheduled and unscheduled results will be included in this analysis.

Measurement	Normal Range
Body mass index	$18 - 35 \text{ kg/m}^2$
Temperature	95-100 °F (35-37.8 °C)
Diastolic blood pressure	60 – 90 mmHg
Systolic blood pressure	90 – 140 mmHg
Heart rate	50 – 100 bpm
Respiration rate	10-25 breaths per minute

Table 3 Vital Signs Normal Ranges

A listing of subjects with abnormalities in vital sign parameters will be presented.

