4.5.5 ECG Data

Twelve-lead ECGs will be collected. Descriptive summaries will be presented for heart rate (bpm), PR interval (msec), QRS duration (msec), uncorrected QT interval (msec), and QTcF (msec).

Normal, abnormal but not clinically significant, and abnormal and clinically significant ECG investigator interpretation results will be summarized and flagged in the listings.

The number and percentage of subjects with post-baseline abnormally low or high values for heart rate, PR interval, and QRS duration based on the normal ranges defined in Table 4 will be presented.

Table 4	ECG Normal Ranges	

Parameter	Low	High
Heart Rate (beats/min)	45	120
PR Interval (msec)	120	220
QRS Duration (msec	80	130

Additionally, the number and percentage of subjects with actual QT and QTcF values \leq 450 msec, 450 msec to \leq 480 msec, 480 to \leq 500 msec, >500 msec and with changes from baseline \leq 30 msec, 30 msec to \leq 60 msec, and >60 msec will be presented.

All ECG results will be displayed in the data listings.

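### SAP 4.5.5 does not bring unscheduled ECGs into the ECG abnormality counts, so under the default in Protocol 7.1 an outlier seen only on an unscheduled tracing is listed but not counted

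*Protocol*

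**What the plan says.** Protocol 7.1 gives the default for every type of measurement: "Unscheduled measurements will be excluded from the descriptive statistics and statistical analysis but will be included in listings". The same section sets the hierarchy: "The statistical analysis methods described in the SAP will supersede the statistical methods described in this protocol".

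The SAP departs from the default in three places, each tied to a count or summary of abnormal values:

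- SAP 4.5.3.1, potentially clinically significant hematology and chemistry values: "All scheduled and unscheduled results will be included in this laboratory analysis".
- SAP 4.5.3.2, abnormal liver enzymes and liver function tests: "All scheduled and unscheduled results will be included in these analyses".
- SAP 4.5.4, abnormally low or high vital signs: "All scheduled and unscheduled results will be included in this analysis".

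SAP 4.5.5 calls for the same kind of output for ECGs: "The number and percentage of subjects with post-baseline abnormally low or high values for heart rate, PR interval, and QRS duration", and then the number of subjects in bands of QT and QTcF (top band above 500 msec) and of change from baseline (top band above 60 msec). It has no sentence on unscheduled results. It says only that every ECG result goes into the listings.

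The protocol expects unscheduled ECGs. Protocol 6.5.4 states: "Additional ECGs may be performed at other times if deemed necessary by the Investigator". Protocol 5.1.7 states that "unscheduled visits may be conducted to perform or repeat assessments, including ECG". Protocol 2.3 names ECGs among the primary safety endpoints.

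**The concern.** Unscheduled ECGs can be taken because the investigator judges one necessary, and unscheduled visits may be held for safety reasons (Protocol 3.1). If those tracings do not feed the abnormality counts, a conduction or repolarization outlier found between visits reaches the clinical study report only as a line in a listing. The summary table that readers rely on (SAP Table 7.3) would not show it.

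The gaps between scheduled ECGs are long enough for this to matter. The visit descriptions place no ECG at Visit 2, the first visit at which the dose may change. From Visit 3 onward ECGs are nominally 8 weeks apart, and adjunctive stimulants are allowed after Visit 4. An unscheduled tracing may be the only one taken near an event.

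The treatment would also be uneven. The SAP admits unscheduled results to laboratory, liver and vital-sign abnormality counts, and gives no reason for handling ECGs differently.

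**Working it through.** The plan states no figure on this point, so there is none to reproduce. The check is a comparison of texts, followed by some arithmetic for scale.

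**Step 1: which rule applies to which output.**

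| Output | Refers to post-baseline values | SAP admits unscheduled results | Rule in force |
|---|---|---|---|
| Significant laboratory values (SAP 4.5.3.1) | yes | yes | SAP: included |
| Liver tests (SAP 4.5.3.2) | yes | yes | SAP: included |
| Abnormal vital signs (SAP 4.5.4) | yes | yes | SAP: included |
| ECG heart rate, PR, QRS (SAP 4.5.5) | yes | silent | Protocol 7.1: excluded |
| ECG QT/QTcF bands (SAP 4.5.5) | no | silent | Protocol 7.1: excluded |

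The SAP supersedes the protocol for methods that the SAP describes. On unscheduled ECGs it describes none, so the default stands. Sending all ECG results to listings is what Protocol 7.1 already prescribes for unscheduled data, so that sentence does not override it.

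**Step 2: direction of the error.** SAP 4.5.5 counts subjects, not tracings. Let S be the subjects with an outlier on at least one scheduled post-baseline ECG, and U those with one on at least one unscheduled ECG. The default reports |S|. Using all tracings gives |S ∪ U|. The difference is the number of subjects in U but not in S, which is never negative. The count beyond a limit can therefore only be too low. For the QT/QTcF bands this applies to the number above each cut-point. A middle band could lose a subject to a higher one.

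**Step 3: spacing of scheduled ECGs.** Protocol 5.1.3 to 5.1.5 place ECGs at Visit 3, Visits 4 to 21 and Visit 22: 1 + 18 + 1 = 20 scheduled post-dose ECGs for a subject who completes. Nominal days run from 29 to 1093, so the interval is (1093 − 29) / 19 = 56 days.

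**Step 4: scale.** The documents do not say how many unscheduled ECGs to expect. Assume that all 366 subjects (the enrolment ceiling) are dosed and in the denominator, that no subject has the outlier on a scheduled ECG, and that k subjects have it only on an unscheduled one. The default reports 0 of 366. One subject is 1/366 = 0.27 percentage points. For zero events the exact two-sided 95% upper limit is 1 − 0.025^(1/366) = 1.00%. The other limits are Clopper-Pearson.

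| k | Reported under the default | With unscheduled ECGs | Exact 95% limits |
|---|---|---|---|
| 0 | 0% | 0% | 0 to 1.00% |
| 1 | 0% | 0.27% | 0.01 to 1.51% |
| 2 | 0% | 0.55% | 0.07 to 1.96% |
| 3 | 0% | 0.82% | 0.17 to 2.38% |

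The plan calls for no confidence intervals; the limits only show scale.

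**The case against.** The strongest objection is that no SAP sentence excludes unscheduled ECGs. SAP 3.2 defines post-baseline as any assessment completed after the first open-label dose, and SAP 4.5.5 counts post-baseline heart rate, PR and QRS. Since the SAP prevails, a programmer could include unscheduled tracings for those three. That reading is available but weaker. SAP 3.2 fixes timing relative to dosing and does not mention unscheduled visits. The laboratory, liver and vital-sign sections also refer to post-baseline values, yet each adds an explicit inclusion sentence. The QT/QTcF sentence does not use the term at all. What stands is that the exclusion follows from SAP silence plus the protocol default, not from an express SAP rule.

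A reader might infer three further things that the documents do not support:

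- That the SAP reverses the protocol rule for laboratory tests and vital signs in general. It does so only for the abnormality analyses. The by-visit summaries (SAP Tables 5.1.2, 5.2.2 and 6.1) have no such sentence.
- That every outlying unscheduled tracing removes a case. It does so only if the subject has no scheduled tracing beyond the same limit. Where an unscheduled ECG repeats an abnormal scheduled one, the scheduled value still counts.
- That vital-sign and ECG heart-rate counts would otherwise agree. Vital-sign heart rate is seated or standing with a normal range of 50 to 100 bpm; ECG heart rate is supine with limits of 45 and 120. They differ by design.

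There are partial safeguards. ECG deterioration that causes symptoms, a change in treatment or discontinuation is an adverse event (Protocol 6.3), syncope is an event of special interest, and SAP Listing 7.2 is dedicated to subjects with ECG abnormalities. None of these puts an asymptomatic outlier into the summary counts. Nor do the documents say that unscheduled ECGs are the most likely to hold an outlier. Some will be confirmatory repeats.

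**Conclusion.** The concern holds in this form: on the better reading of the two documents, a subject whose only abnormal ECG value is on an unscheduled tracing is listed but not counted. This affects a primary safety endpoint, and the counts can err only toward apparent safety.

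Its size cannot be stated. At 366 subjects each affected subject is worth 0.27 percentage points, assuming that all 366 are in the denominator. The number affected could be zero, and Protocol 1.2.1 reports no effect on QTcF after multiple 1800 mg doses. The point matters because these events are rare and a change from none to one is noticed.

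The conclusion rests on treating SAP silence as leaving Protocol 7.1 in force. If the SAP 3.2 reading were adopted instead, heart rate, PR and QRS would be covered and the QT/QTcF bands would still be unsettled. The plan needs a sentence under either reading. It should be changed, but no data are lost and the design is unaffected.

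**What to change.** Add to SAP 4.5.5 wording to this effect: *Every valid ECG recorded after the first dose, whether scheduled or unscheduled, is used in the counts of subjects with abnormally low or high heart rate, PR interval and QRS duration (low and high counted separately) and in the QT and QTcF value and change categories (each subject classified by the highest post-baseline value and by the largest increase from baseline). By-visit summaries in Tables 7.1 and 7.2 use scheduled ECGs only. For these counts this supersedes Protocol 7.1.*

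Counting low and high separately is needed because three parameters have two limits. The word valid is needed because Protocol 6.5.4 has invalid measurements repeated.

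The cost is a short SAP addition and a changed filter in the program for Table 7.3. No new data are collected. The counts may be slightly less favourable, and subjects with more tracings have more chances to cross a limit. The SAP already accepts that for laboratory and vital-sign counts.

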### 7.2. Handling of Missing Data

If applicable, missing efficacy data will be imputed using multiple imputation.

Missing dates for occurrence of adverse events and non-study medication use will be imputed using the following rules:

- 1. Start dates with both missing day and month will be set to the 1st of January of that year, except as noted in rule 4 below. End dates with both missing day and month will be set to the 31st of December of that year.
- 2. Start dates with missing day only will be imputed with the first day of the month, except as noted in rule 4 below. End dates with missing day only will be imputed with the last day of the month.
- 3. Start dates with missing month only will be imputed by setting the month to January of the year. End dates with missing month only will be imputed to December of the year.
- 4. If a start date has missing day only with month and year the same as the month and year of the first dose date, then the start date will be set to the first dose date. If a start date has missing day and month with the year the same as the year of the first dose date, then the start date will be set to the first dose date.

### 7.3. Analysis Populations

The **Safety Population** is all subjects who are enrolled and receive at least one dose of SM. All statistical analyses will be based on the Safety Population.

### 7.4. Demographics and Baseline Analysis

Demographic/baseline variables including age, age group, sex, ethnicity, race, height and weight at Visit 1, and BMI will be summarized using descriptive statistics for continuous variables and using counts and percentages for categorical variables. The descriptive summary will be presented by optimized dose group and overall for the Safety Population.

### 7.5. Subject Disposition

A disposition of subjects will include the number and percentage of subjects in the Safety Population.

The number and percentage of subjects who completed and discontinued from the study and primary reason for early discontinuation will be summarized. The reason for early discontinuation may include any of the following:

- Withdrawal of consent
- Noncompliance
- Occurrence of unmanageable AEs
- Lost to follow-up
- Related to COVID-19
- Other

### 7.6. Study Medication Exposure and Compliance

Duration of exposure is defined as the total number of days a subject is exposed to any SM. This will be calculated for each subject by taking the difference between the date of last dose minus the date of the first dose, plus 1 (date of last dose minus date of first dose +1).

Duration of treatment exposure will be summarized by duration category and will also be summarized using descriptive statistics (n, mean, SD, median, minimum, and maximum).

Percent of SM compliance is defined as {(number of capsules dispensed minus number of capsules returned) / X × (date of last dose minus date of first dose + 1)}\* 100%, where 'X' is equal to the number of capsules that the subject was instructed to take daily during the treatment period (i.e., between visits).

% SM compliance = 
$$\left[\frac{(no. of capsules dispensed) - (no. of capsules returned)}{X \times [(date of last dose) - (date of first dose) + 1]}\right] \times 100$$

For each treatment, SM compliance will be summarized by compliance category (<80%, 80-120%, and >120%) and number of subjects in each compliance category. Study medication compliance will also be summarized as a continuous variable using descriptive statistics (n, mean, SD, median, minimum, and maximum) for each treatment.

